1.0 Background

Prostate cancer (PCa) is the most common non-cutaneous malignancy and the second leading cause of death among men.¹ Transrectal ultrasound guided prostate biopsies are currently the gold standard for the diagnosis of PCa which can be categorized as clinically significant or indolent PCa. Clinically significant prostate cancer (csPCa) is deemed cancer which warrants treatment and is defined according to previously published studies as biopsy Gleason score ≥ 7 or maximum cancer core length ≥ 5 mm.² Indolent PCa is considered cancer which does not require treatment with patients placed on active surveillance and is defined by the modified Epstein criteria as biopsy Gleason score ≤ 6 , PSA density ≤ 0.15 , ≤ 2 positive cores, and unilateral cancer).^{2,3} Given concerns regarding the overtreatment of indolent PCa, efforts to improve the diagnosis of csPCa and limit diagnosis of indolent disease are needed.⁴

Standard in-office prostate biopsies using transrectal ultrasound guidance are random, non-diagnostic and imprecise in detecting PCa. Moreover, standard biopsies may miss csPCa. With multi-parametric magnetic resonance imaging (mpMRI), we now have a way of increasing the detection of csPCa while decreasing the detection of indolent disease. Using the mpMRI and scoring methodology called the prostate imaging reporting and data system (PIRADS v2), lesions suspicious for PCa and csPCa can be categorized as: 1: very low, 2: low, 3: intermediate, 4: high, and 5: very high risk of csPCa.⁵ Studies using mpMRI recommend prostate biopsy of mpMRI lesions with PIRADS ≥ 3 .^{2,5,6}

The Division of Urology has introduced a powerful new solution for analysis, planning and targeted biopsy of the prostate. This consists of using DynaCAD for Prostate mpMRI and the UroNav fusion biopsy system- a comprehensive solution which offers a cutting edge imaging option for many patients with clinical suspicion for harboring PCa mainly by elevated and/ or rising prostate specific antigen (PSA) levels. Targeted MRI/Ultrasound biopsy is poised to become the new standard in PCa diagnosis at UTMB.

Presently at UTMB, if patients have a mpMRI and region of interest identified (usually mpMRI obtained after prior negative biopsy or in patients deemed to have indolent disease by standard prostate biopsy and to be placed on active surveillance) then they are referred for consideration of targeted biopsy with UroNav.

No study has compared UroNav transperineal mpMRI-targeted versus standard transrectal ultrasound guided prostate biopsy in the detection of prostate cancer. A recent trial compared transperineal/transrectal mpMRI-targeted versus TRUS systematic biopsy in biopsy naïve men and noted improved detection of csPCa.⁷ Specifically, the overall (50.5% vs 29.5%, $p=0.002$) and csPCa (43.9% vs 18.1%, $p<0.001$) detection rates were significantly higher in the targeted versus the standard transrectal ultrasound guided prostate biopsy group, respectively.⁷ While this trial provided the first level one evidence in support of mpMRI-targeted biopsy in biopsy naïve men, the study used a device not

commercially available in the United States and allowed both transperineal or transrectal mpMRI-targeted prostate biopsies to be performed in the targeted biopsy arm of the study.

In this prospective randomized trial, the investigators will assess the detection rates of csPCa diagnosis of standard transrectal ultrasound guided prostate biopsy compared to computer targeted system (UroNav - InVivo corp) to sample suspicious areas (PIRADS ≥ 3) identified on mpMRI.

The hypothesis being tested is that computerized fusion guided biopsy (UroNav) will increase detection of csPCa compared to standard transrectal ultrasound guided prostate biopsy alone.

2.0 Rationale and Specific Aims

Transrectal prostate biopsy with multiple samples using a standardized template under transrectal ultrasound (TRUS) guidance is the current standard diagnostic approach in suspicion of PCa as recommended by the European Association of Urology (EAU) and American Urological Association (AUA).^{8,9} With the introduction of mpMRI we now have an effective way to localize cancer and direct our biopsies more effectively.⁶ mpMRI guided biopsies have shown to have high negative predictive values, especially in men with prior negative mapping results.^{10,11} mpMRI-targeted biopsy and systemic biopsies are comparable in their detection rates of PCa, with mpMRI showing increasing csPCa detection in biopsy-naive patients, thus decreasing the detection of indolent PCa.

The mpMRI-targeted biopsy system UroNav allows for the fusion of mpMRI images with live TRUS feed to target lesions noted on mpMRI. Studies have demonstrated men undergoing biopsy for suspected PCa, targeted MR/ultrasound fusion biopsy (using the transrectal UroNav prostate biopsy device), compared with standard extended-sextant TRUS-guided biopsy, was associated with increased detection of high-risk PCa and decreased detection of indolent disease.⁶

The mpMRI-targeted devices used in prior studies have been either the UroNav transrectal machine or used a combination of transrectal and transperineal techniques using devices not available in the United States.^{6,7} Based on these prospective studies and limited randomized trials there is increasing support of the utility of using mpMRI-targeted prostate biopsy in the detection of PCa.

The present study will assess a transperineal device (UroNav) currently available in the United States and thus will not only directly assess the impact of transperineal prostate detection of csPCa but provide the first United States trial assessing the utility of this platform. UTMB has the *only* commercially available UroNav transperineal mpMRI-targeted device in the state of Texas. Thus, this trial has the leverage of a large academic primary care referral network combined with a novel device to provide important clinical

information discerning the improved detection of csPCa in a relatively short period of time (approximately one year).

The UroNav fusion biopsy system until recently *only* allowed targeted prostate biopsy to be performed transrectally. With over 200 devices sold in the United States, UroNav is the most commonly used targeted biopsy system and has been extensively studied by the National Institutes of Health (NIH). UroNav requires pre-biopsy mpMRI for lesion(s) delineation, real-time TRUS registered to the mpMRI and electromagnetic tracking of biopsy needles for precise guidance. The actual working elements of the UroNav fusion biopsy system includes the UroNav mobile workstation cart, ultrasound cart and the electromagnetic field generator which connects to the patient bed by a mobile arm. The electromagnetic field generator in combination with a navigation sensor mounted to the TRUS transducer merges the mpMRI images with live TRUS guidance to accurately biopsy the prostate. As previously mentioned, UroNav provides support for transrectal biopsy procedures but *now* has the capability to perform biopsy via a transperineal approach. The UroNav fusion-guidance for transperineal biopsy requires the transperineal stepper which holds the TRUS probe and a standard biopsy grid plate equipped with UroNav universal sensors to precisely perform biopsies. Invivo supports both UroNav and DynaCad which UTMB has recently acquired and the Department of Radiology currently has been working with for many years, respectively. DynaCad is a software used in the radiology suite which exports diagnostic 3D information from a prior mpMRI exam to discern the prostate gland and MR-suspicious lesions. The transperineal approach (skin halfway between scrotum and anus) essentially eliminates the risk of sepsis and/or infection associated with transrectal prostate biopsy samples obtained through feces and rectal mucosa. Sepsis occurs in up to 3% of patients who undergo transrectal prostate biopsy (Table 1).¹²

Table 1. Signs and Symptoms of Sepsis¹²

General Fever (>38.3°C) Hypothermia (<36°C) Tachycardia >90/min Tachypnea Hypotension (SBP<90 mmHg) Altered mental status Significant edema or positive fluid balance Oliguria Ileus Altered mental status/lethargy
 
Laboratory Normal WBC with >10% immature forms Creatinine increase >0.5 mg/dL INR >1.5 or aPTT >60 secs

Thrombocytopenia (platelet count <100,000/mm³)
Hyperglycemia (plasma glucose >120 mg/dL) in the absence of diabetes
Hyperlactatemia (>1 mmol/L)

No study has compared UroNav transperineal mpMRI-targeted versus standard transrectal prostate biopsy in the detection of prostate cancer.

The **hypothesis** being tested is that computerized fusion guided biopsy (**UroNav**) will increase detection of csPCa compared to standard biopsy (SB) (transrectal) alone. The primary end point will be the comparison of detection rates csPCa between arm A mpMRI+ and arm B (refer to figure on page 9). csPCa will be defined according to the Standards of Reporting for MRI-targeted Biopsy Studies (START) criteria for targeted biopsy Gleason Score ≥ 7 or maximum cancer core length (CCL) ≥ 5 mm and the updated Epstein criteria for SB (Gleason score ≥ 7 , PSA density ≥ 0.15 , Gleason score ≥ 2 positive cores, and bilateral cancer).^{2,3} The secondary end points will be (1) comparison of the overall detection rate of PCa and csPCa between arm A mpMRI+, arm A mpMRI-, and arm B and (2) comparison of complication rates (Table 2) between arm A mpMRI+ and arm B.

Considering 10% of patients will be lost to follow-up, the total sample size needed will be 80 patients (See Section 9.1 Statistical Considerations). The clinical trial is enrolled in clinicaltrials.gov (**ClinicalTrials.gov Identifier NCT03044197**).

If the primary end point is reached, the study will continue and remain ongoing to examine the remaining secondary end points.

Specific Aims:

1. Determine if UroNav increases the detection of csPCa between arm A mpMRI+ than arm B standard transrectal biopsy.
2. Determine if UroNav increases the overall detection of PCa between arm A mpMRI+ versus arm A mpMRI- and arm B standard transrectal biopsy.
3. Determine if UroNav decreases rates of complications between arm A mpMRI+ than arm B standard transrectal biopsy.

3.0 Inclusion/Exclusion Criteria

Subjects must meet all of the inclusion criteria in order to be eligible to participate in the study.

1. Males aged 18-75 years old
2. PSA >1 ng/ml but <15 ng/ml
3. Negative DRE

4. Subject has provided informed consent in a manner approved by the IRB and is willing and able to comply with the trial procedures.

Subjects meeting any of the exclusion criteria at baseline will be excluded from study participation.

1. Previous prostate biopsy or prostate surgery
2. Previous prostate mpMRI
3. Contraindication to mpMRI: Patient has implanted metal clips or wires of the type which may concentrate radiofrequency fields or cause tissue damage from twisting in a magnetic field. Examples include: aneurysm clip, implanted neural stimulator, implanted cardiac pacemaker or autodefibrillator, cochlear implant, ocular foreign body (e.g., metal shavings), any implanted device (pumps, infusion devices, etc), shrapnel injuries.
4. Patients in the Texas Department of Criminal Justice (prisoners)
5. Patients with acute urinary symptoms including urinary retention and urinary tract infection
6. Patient has dialysis dependent renal failure or baseline serum creatinine level > 2.0mg/dL

4.0 Treatment Assignment/Randomization

Enrollment into the study is defined as following randomization. Patients who fulfill all eligibility criteria and have provided written consent will be randomized to undergo mpMRI followed by targeted biopsies (arm A mpMRI+) or TRUS transrectal biopsy (arm-B) by the PI and authorized study collaborators. [REDACTED], study coordinator, will have access to randomization, generated by an electronic randomization system provided by REDCap.

Sequence generation

Patients will be randomly assigned to arm A or arm B following a 1:1 simple randomization procedure according to a computer-generated randomization list provided by REDCap. [REDACTED] [REDACTED] study coordinator, and a designated back-up will be the only persons to have access of the REDCap randomization list.

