5.0 Study Procedures

Study population and design:

Eligible patients referred to the Division of Urology will be randomly assigned to one of the following arms: **arm A (mpMRI+ group)**, mpMRI prior to transperineal mpMRI-targeted prostate biopsy; **arm B (Standard group)**, TRUS-guided transrectal 12-core prostate biopsy.

In arm A, all patients with positive mpMRI evidence of lesions suspicious for PCa, i.e. PI RADS ≥ 3 will be submitted to transperineal MRI-targeted prostate biopsy (arm A mpMRI+). In cases of negative mpMRI results i.e. PI RADS < 3, arm A patients will

undergo TRUS-guided transrectal 12-core prostate biopsy (arm A mpMRI-)(refer to figure on page 9).

[figure not shown]
The present randomized clinical trial will compare the outcomes between the two arms.

Primary End-Points: The primary end point will be the comparison of detection rates csPCa between arm A mpMRI+ and arm B. csPCa will be defined according to the Standards of Reporting for MRI-targeted Biopsy Studies (START) criteria for targeted biopsy Gleason Score ≥ 7 or maximum cancer core length (CCL) ≥ 5 mm and the updated Epstein criteria for standard biopsy (Gleason score ≥ 7 , PSA density ≥ 0.15 , Gleason score ≥ 2 positive cores, and bilateral cancer).^{2,3} Patients will be enrolled in an intention to treat trial (See Section 9.1 Statistical Considerations).

Secondary End-Points: The secondary end points will be:

- i. Comparison of the overall detection rate of PCa and csPCa between arm A mpMRI+, arm A mpMRI-, and arm B and
- ii. Comparison of complication rates (Table 2) between arm A mpMRI+ and arm B.

If the primary end point is reached, the study will continue and remain ongoing to examine the remaining secondary end points.

Patients will be consented by Urology providers (IRB approved Co-Investigators and collaborators).

Randomization and data collection will be done by [REDACTED] [REDACTED] (study coordinator) into a REDCap generated case form (SEE APPENDIX). Study coordinator will provide de-identified data for statistical data analysis and will have master file, in password protected computer, which will link the PHI to subject ID (will be assigned by the study coordinator). After the completion of statistical analysis the master file will be deleted permanently.

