Data analysis will be done by [name] (Department of Surgery analyst) supervised by [name] (PI) and statistical analysis collaborators ([name], IRB approved). Data to be analyzed will be de-identified will have no protected health information (PHI) including patient name, medical record number or date of birth.

PRE-PROCEDURE EVALUATION (within 2 months from study enrollment)

Patients are going to be evaluated at the time of office appointment by the PI and Study Collaborators

- Screening-Patients with elevated level of Prostate-specific antigen (PSA >1 ng/ml but <15 ng/ml), will be screened for research study participation by the urology providers (Co-Investigators) and [name] (PI).
- Inclusion/ Exclusion Criteria
- Consent- Patient having all the inclusion and no exclusion criteria for eligibility will be approached with research consent for participation by the urology providers (Co-Investigators) and [name] (PI).
- Demographics
- Medical History
- Surgical History
- Clinical Stage/ Digital Rectal Exam
- Vital Signs
- Physical Exam
- MRI PI-RAD Score (Grade System to classifying prostate cancer , using Pre-Procedure MRI (within 2 months from consenting & randomization))- only required for arm A
- Gland Volume (Calculated from the mpMRI and/or Ultrasound -within 2 months from consenting & randomization)
- Prostate specific antigen (PSA)

PROCEDURE EVALUATION (Surgical procedure)

Patient will undergo prostate biopsy in arm A or arm B as assigned by the randomization card

- A. Transperineal mpMRI-targeted prostate biopsy (arm A mpMRI+) (Procedure will be performed in operating room):** mpMRI-targeted prostate biopsy is standard of care and will be performed using the UroNav transperineal fusion system by a single urologist ([name]). [name] has >1 yr experience in performing mpMRI-targeted prostate biopsies. All patients will receive one dose of Ancef intravenous antibiotic at time of surgery (Vancomycin 1gm intravenous for penicillin/cephalosporin allergies or prior history of orthopedic hardware implanted within 2 years) to cover skin flora and may add additional antibiotic if prior documented UTI(s) in past then antibiotic may be tailored according to those culture(s) sensitivities) to cover enteric flora as well. All patients will receive an enema until result to be performed the morning of prostate biopsy.

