(PI). All patients will receive one dose fluoroquinolone antibiotic to be taken the morning of prostate biopsy (if fluoroquinolone allergy then may substitute Bactrim DS, if prior documented UTI(s) in past then antibiotic may be tailored according to those culture(s) sensitivities) to cover enteric flora. All patients will receive an enema until result to be performed the morning of prostate biopsy.

Urologists will obtain SOC informed consent and perform the TRUS biopsies.

The 12 cores will be obtained from 12 separate anatomical regions of the prostate which is standard practice in performing TRUS-guided transrectal prostate biopsy: left medial apex, left lateral apex, left medial midgland, left lateral midgland, left medial base, left lateral base, right medial apex, right lateral apex, right medial midgland, right lateral midgland, right medial base and right lateral base.

For arm A and arm B biopsy, [REDACTED] (the study research coordinator) , [name] and [name] (Chairman, Division of Urology and study co-investigator), will monitor safety and any possible Unanticipated Adverse Device Events (UADEs). Serious Adverse Events (SAEs), Adverse Events (AEs) and UADEs assessment will be done by [name].

For Arm A and Arm B biopsy, the procedure will be performed and the sample will be sent to the Pathology lab for analysis. [name] and other urology providers will not be involved with the sample analysis and biopsy report data and results. Once the report / data is available on Epic for review, the study coordinator will extract data from patient records/ Epic into an electronic data sheet (REDCap case form, SEE APPENDIX) on which the patient will be identified by a subject ID assigned to them, no PHI information will be present. The data analysis will be performed in aggregate. A master file linking the patient to Subject ID will remain with the study coordinator for data entry purposes and once the data analysis is complete, the master file will be securely stored and password protected.

- Adverse event assessment (Tables 2 and 3)

POST-PROCEDURE EVALUATION/ END OF STUDY- (Follow-up can be done by telephone or clinical visit)

- Diagnosis of csPCa- Based on the biopsy report will be available 2-4 weeks post-procedure
- Gleason score ((Grade System to classifying PCa)- Based on the biopsy report will be available 2-4 weeks post-procedure
- Total cancer core length (mm)- Based on the biopsy report will be available 2-4 weeks post-procedure

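### Allocation concealment is not assured: the coordinator who randomises and collects data in this open trial also has access to the randomisation list, and the release of assignments is not described

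*Combined protocol and SAP*

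**What the plan says.** **Sequence and access.** Section 4.0 specifies 1:1 simple randomisation from a computer-generated list in REDCap, with no blocks or strata. On access it says: "study coordinator, and a designated back-up will be the only persons to have access of the REDCap randomization list".

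**Who randomises.** In Section 5.0, "Randomization and data collection will be done by" is followed by a redacted name identified as the study coordinator. Section 4.0 also gives the coordinator access to randomisation. The preceding sentence there, however, has men randomised to targeted biopsy "or TRUS transrectal biopsy (arm-B) by the PI and authorized study collaborators".

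**Who recruits.** Section 5.0: "Patients will be consented by Urology providers (IRB approved Co-Investigators and collaborators"). Patients "will be screened for research study participation by the urology providers (Co-Investigators") and the PI.

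**Order of events.** Section 4.0: "Patients who fulfill all eligibility criteria and have provided written consent will be randomized". Enrolment is defined by randomisation.

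**Who collects the outcomes.** Section 5.0: once the biopsy report is available, "the study coordinator will extract data from patient records/ Epic into an electronic data sheet".

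**Blinding and release.** Section 9.0 describes the trial as un-blinded. Under the procedure evaluation, Section 5.0 says that a randomisation card assigns the arm, but no other section explains the card.

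**The concern.** An electronic system conceals allocation only if the person about to make an assignment cannot look it up first. Here one role can open the list, makes the assignment and collects the data. A person who knows the next assignment can decide when a consented man is randomised, or in what order two consented men are taken, or can tell a recruiter what comes next. Any of these could make the arms differ in baseline risk in a way that analysis cannot reliably repair. The trial is open and small (80 men planned), so there is no blinding to limit the motive and little room to absorb an imbalance. A reader of the eventual report will ask whether allocation was concealed, and the plan as written does not let the sponsor answer yes.

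**Working it through.** No significance level, power, event rate or sample size enters this point, so there is no figure to reproduce. The check is to set the sections side by side and ask who could know the next assignment and what that person could do with it.

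1. **Who has the list?** The coordinator and a back-up, and by the word only, nobody else (Section 4.0).
2. **Who makes the assignment?** The coordinator (Section 5.0). So one of the two people with access also randomises. The back-up's tasks are not stated, so the same cannot be shown for that person.
3. **Are upcoming entries hidden?** Not stated. Access to a randomisation list naturally suggests access to the whole list, but the text does not say that future rows can be seen.
4. **How is an assignment released?** Not stated. Eligibility and written consent come before randomisation, but no section says that they must be recorded in REDCap before the arm appears.
5. **Could the recruiters know the next assignment unaided?** Not from the list, which they do not hold. Nor from past assignments: under 1:1 simple randomisation each assignment is independent of those before it, so the best guess is right with probability 1/2 whatever the history. The list is therefore the only route to foreknowledge, and it runs through the coordinator and back-up.
6. **What could the coordinator do with it?** Delay or reorder the randomisation of consented men, or pass on the next assignment. The plan sets no interval between consent and randomisation and no rule that men are randomised in order of consent. It describes no log of men consented but not randomised. The case form in the appendix is not reproduced in the text reviewed, so such a log may exist there.
7. **Do the sections agree on who randomises?** Section 5.0 is clear that the coordinator does. The closing phrase of the sentence in Section 4.0 can attach either to the randomising or to the performing of the biopsies. The first reading conflicts with Section 5.0. The second fits the later statement in Section 5.0 that the PI and co-investigators perform the transrectal biopsies. The randomisation card adds a third, undefined element.

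Steps 1 to 4 establish the gap. Steps 5 and 6 show where it lies and how narrow it is.

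Sample size is untouched. The 31 per arm for Aim 1, the 72 in total for Aim 2 and 72/(1 − 0.10) = 80 do not depend on who can see the list.

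**The case against.** The strongest reply is that the plan already keeps the list from those who choose patients. The urology providers and PI screen and consent, the list is closed to them, consent comes first, and unblocked simple randomisation gives them nothing to predict from. All of this stands, and it is a real partial safeguard. It does not cover the person who releases the assignment, and the plan says nothing about that step.

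A reader might infer several stronger points that the documents do not support:

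- **That assignment is not concealed.** This would need future entries to be visible and knowledge of them to reach the selection or timing of patients. Neither is stated.
- **That Sections 4.0 and 5.0 contradict each other on who randomises.** The Section 4.0 phrase is ambiguous. It needs clarifying, but a contradiction is not established.
- **That the PI has a stake as operator of the targeted procedure.** The operator's name is removed, so this cannot be confirmed.
- **That outcome extraction by the coordinator is part of the concealment problem.** It concerns ascertainment and is a separate matter. It is limited for Gleason score and core length, which come from the pathology report, although the documents do not say that pathologists are blinded to arm.
- **That the bias can be sized by moving a few men with clinically significant cancer between arms.** That status is unknown at randomisation: eligible men have a negative rectal examination and no earlier biopsy or prostate mpMRI. Steering could act only on weaker predictors such as PSA, and the plan gives no figures from which to calculate the effect.

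**Conclusion.** The concern holds in limited form. Concealment is not assured and is vulnerable at the coordinator, because one person can access the list, randomises and collects data in an un-blinded trial, and no safeguard on the release of assignments is described. Bias would require the coordinator to time randomisations or to disclose the next assignment. The documents give no sign that this occurs and no provision that prevents it. Its size cannot be computed.

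The conclusion assumes that access to the list means more than permission to request the next assignment. If REDCap is already set up so that neither person can see future rows, the defect is one of description only, and one sentence would cure it. On either reading the point should be corrected. It does not by itself invalidate the design.

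**What to change.** 1. Have the list generated and loaded into REDCap by a statistician who does not recruit, randomise or collect data, and who does not share it with the PI. This last condition matters because Section 5.0 places the data analyst under the PI's supervision, and the PI screens and consents.
2. Give the coordinator and back-up only the right to randomise the next man, with no view of the list.
3. State that REDCap releases each assignment only after eligibility and consent have been recorded in it.
4. Clarify Sections 4.0 and 5.0: name the one role that randomises, say whether the reference to the PI and collaborators concerns randomisation or biopsy, and define the randomisation card or remove it.

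The cost is a change of REDCap user rights and a few sentences in the protocol. Sample size and analysis do not change.
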